### 12.4 Data analytic plan

***Aim 1:** To determine the impact of low-dose tamoxifen on surrogate endpoint biomarkers of BC risk.*

**Mammographic breast density (MBD).** MBD is the ratio of absolute density to the total breast area. Since participants are randomized, we expect MBD to not differ by treatment status at baseline ( $t_0$ ). However, we will evaluate the success of randomization by examining between group differences in demographic and clinical characteristics (i.e. age, radiation dose, age at radiation exposure), study site, as well as the average MBD of the two breasts (or the available one) at baseline. If imbalance is evident, analysis will take into account the covariates with significant imbalance.

Using an intention-to-treat analysis, the efficacy of low dose tamoxifen in reducing MBD will be compared between patients in the low dose tamoxifen intervention and placebo group by applying the linear mixed effects model for bivariate normally distributed data [103]. All patients with a minimum of baseline ( $t_0$ ) mammographic data will be included in the analysis. MBD data from each breast will be square root transformed (RTMBD) to normality before model fitting. RTMBD for each breast will be modeled by the unstructured mean model using two indicator variables of time. We will assume the effects of time on RTMBD to be the same in both breasts by setting their coefficients equal. Correlation between the breasts will be introduced by assuming a bivariate normal random intercept model with a common fixed effects intercept and breast-specific random effects. Residual errors will be assumed to be bivariate normally distributed with mean zero and non-zero correlation. Unstructured and compound symmetry covariance structures will be considered for residual errors. The fixed effects intercept will be allowed to differ between treatment groups. Interactions of the time indicators with treatment indicator (0 for placebo, 1 for tamoxifen) will be included to allow for treatment

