differences at t1 and t2, and their significance tested using a 2-df chi-square test. Low dose tamoxifen will be considered effective if 1) the 2-df test is significant and the expected RTMBD is lower both at t1 and t2 or at t2 compared to that of the placebo group, or 2) the interaction term at t2 is significant and the expected RTMBD there is lower than that of placebo. It should be noted that because common fixed effects for intercept and time coefficients are assumed for both breasts, the expected RTMBD is the same for both breasts within a treatment group. This model enables use of the data from both breasts to estimate the common treatment effect while accounting for the between-breast correlation and the correlation among repeated measurements over time within a woman. The validity of these restrictions, e.g. common intercept and treatment effect between left and right breast, while biologically reasonable, will be examined and tested. This method also enables women with incomplete RTMBD data, i.e. data from only one breast or missing data at specific time points, to be included in the analysis. In addition to the unstructured mean model, we will also fit a linear model in time, with an interaction of time by group indicator to allow for treatment difference. A significant time by group interaction, with a larger negative slope for the low dose tamoxifen group compared to placebo, will indicate the effectiveness of low dose tamoxifen in reducing MBD.

In addition to unadjusted analyses which are appropriate under the randomization principal, adjusted analysis also will be performed. Significantly imbalanced covariates and covariates known to be prognostic for BC, such as radiation dose, age at irradiation, premature menopause, and family history for BC, will be incorporated in the longitudinal models before including and testing the time by treatment group interaction.

To address potential noncompliance, we will also conduct an as-treated analysis, considering patients' actual treatment uptake. Instead of the treatment indicator (PBO or LDTAM), we will include adherence rate, i.e. 0 for PBO and a number between 0 and 1 for LDTAM determined by pill count, in the LME model. Time-specific adherence rate and the overall adherence rate will be considered. If LDTAM is effective, we may expect to see a decrease in MBD with adherence rate.

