The expected RTMBD at the three time points in the pre-menopausal and post-menopausal women in the Puget Sound sample were estimated longitudinally using SAS Proc Mixed with a compound symmetry covariance structure. Square root transformation was used to normalize the distribution. A significant decline in MBD with time was detected. Since the covariance matrices of the pre- and post-menopausal women looked very similar, for simplicity, they were assumed to be equal. To determine the variance/covariances of the MBDs and the expected values at t0, t1, t2 in the anticipated CAYAC sample, 1000 random trials of size n were generated from multivariate normal distributions with parameters estimated from the Puget Sound sample to simulate the CAYAC sample expected to contain 67% pre-menopausal and 33% post-menopausal women. Sixty-seven percent of n were drawn randomly from a multivariate normal distribution with expected MBD of (24.7, 23.57, 22.27) at (t0, t1, t2) as predicted for Puget sound pre-menopausal women, and 33% of n were drawn randomly from a multivariate normal distribution with expected Y of (15.49, 11.99, 13.03) as predicted for post-menopausal women. For each of the 1000 simulated samples, a longitudinal linear model was fitted assuming a compound symmetry structure for the covariance. The average of the 1000 estimates of the linear parameter was used to estimate the expected RTMBD at t0, t1, t2 for the CAYAC control sample.

The expected RTMBDs for CAYAC controls obtained from simulations were used to specify the effect size, defined as the difference between expected values at t2 for the two groups divided by the common sd, in the longitudinal power calculations were conducted using the program RMASS2. [107]. We assumed a Type I error of .05, power of .80, 2-sided test, no attrition over time, linear trend, compound symmetry covariance structure, and a correlation of 0.8 between measurements (estimated from the Puget Sound sample).

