The size of the difference in MBD that can be detected between the low dose tamoxifen and placebo groups at year 2 (t2) are shown in the table below. Column 4 indicates the expected MBD before randomization (at t0). The expected MBDs at t2 for the control and treatment groups are shown in columns 5 and 6, respectively. Column 7 and Column 8 are the % reduction in MBD at t2 relative to t0 in the placebo control group and low dose tamoxifen treatment group, respectively. The last column shows the % reduction in PD in the treatment group at t2 relative to controls.

Placebo (PBO)	Low Dose Tamoxifen (LDTAM)	Power	Exp(MBD) at t0	Exp(MBD) at t2		% reduction in MBD at t2 relative to t0		% reduction in MBD at t2 for LDTAM group relative to PBO
			Both treatment groups	PBO	LDTAM	PBO	LDTAM	
50	50	.8	21.2	18.75	13.42	11.6%	36.5%	28.4%
		.9	"	"	12.68	"	40.0%	32.4%
75	75	.8	21.1	18.67	14.27	"	32.5%	23.5%
		.9	"	"	13.70	"	35.2%	26.6%
100	100	.8	21.2	18.72	14.89	"	29.6%	20.5%
		.9	"	"	14.32	"	32.3%	23.5%
150	150	.8	21.1	18.64	15.47	"	26.8%	17.0%
		.9	"	"	15.00	"	29.1%	19.5%
200	200	.8	21.1	18.67	15.91	"	24.8%	14.8%
		.9	"	"	15.50	"	26.7%	17.0%

If we anticipate the MBD in the low dose tamoxifen group to change from 21.1 at t0 to 14.89 at t2 compared to 18.72 at t2 in controls (in other words, a reduction of ~30% with low dose tamoxifen versus 11.6% with placebo over a 2 year time, or about 20% reduction in MBD with low dose tamoxifen relative to placebo, or an effect size of 0.25 at t2), a sample size of 100 per arm will be able to detect this magnitude of change with 80% power. With 10% attrition at each annual follow-up visit, 115 women per arm (or a total of 230) would be required. Thus, the goal accrual for this trial will be 115 women per arm, for a total of 230 women at t0.

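### The supplementary as-treated analysis replaces the randomised arm with pill-count adherence, so its coefficient can show false benefit or false harm, or hide a real benefit

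*Combined protocol and SAP*

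**What the plan says.** Section 12.4 makes the main comparison by randomised arm: "Using an intention-to-treat analysis, the efficacy of low dose tamoxifen in reducing MBD will be compared" between the two groups. The criteria for calling the drug effective (the 2-df test, the year-2 interaction and the linear slope) all use time-by-arm terms.

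A further analysis follows: "To address potential noncompliance, we will also conduct an as-treated analysis, considering patients' actual treatment uptake". Its model is described as "Instead of the treatment indicator (PBO or LDTAM), we will include adherence rate", coded "0 for PBO and a number between 0 and 1 for LDTAM determined by pill count", either for each time point or overall. The paragraph closes with "If LDTAM is effective, we may expect to see a decrease in MBD with adherence rate".

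That paragraph names no instrument, no covariate adjustment and no caution about confounding. The adjusted analyses described just before it are not said to extend to it. Under Treatment adherence, the same section plans three-monthly pill counts and a comparison of compliance between arms, so placebo adherence will be known. The as-treated model does not use it.

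**The concern.** Randomisation protects the comparison of arms. It does not protect a comparison of women who took most of their capsules with women who took fewer. Section 12.4 itself lists attained age, menopausal status, body mass index and prior hormone use among factors that affect density, and any of these could also influence adherence. If women who adhere well would have lost more density without the drug, the model credits that loss to tamoxifen. If they would have lost less, it masks a real effect or suggests harm.

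At stake is the answer to a secondary question: what the drug does when it is taken. The planned coefficient does not isolate that effect, although data already being collected allow a less biased estimate.

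**Working it through.** **1. The plan's own figure.** Section 12.5 states "We assumed a Type I error of .05, power of .80, 2-sided test, no attrition over time", "a correlation of 0.8 between measurements" and "an effect size of 0.25 at t2", with 100 women per arm. Under compound symmetry the SD of the two-year change is √(2 × (1 − 0.8)) = 0.632 SD. Then n = 2 × 0.4 × (1.96 + 0.842)² / 0.25² = 100.5 per arm, which agrees with 100.

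On the square-root scale the planned difference is √18.72 − √14.89 = 0.468. The implied SD is 0.468 / 0.25 = 1.87, and the SD of change is 1.87 × 0.632 = 1.18.

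**2. The as-treated slope when the drug does nothing.** Let A be 0 for placebo and have mean m and SD s on tamoxifen, with equal arms. I take adherence to replace the arm in the time interaction, use overall adherence and assume complete data. Then

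- Var(A) = 0.25 m² + 0.5 s²
- expected slope = 0.5 × Cov(A, change within tamoxifen) / Var(A)

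The slope is zero only if adherence is unrelated to natural density change.

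**3. Inputs.** Section 12.5 assumes 90% adherence on placebo and gives about 77% as the detectable rate on tamoxifen. The mean of 0.80, all SDs and all correlations are assumptions.

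Worked case: m = 0.77, s = 0.3, and an assumed latent correlation of 0.3 (0.26 as realised on the bounded adherence scale).

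- Numerator: 0.5 × 0.26 × 0.3 × 0.632 = 0.0246
- Denominator: 0.25 × 0.593 + 0.5 × 0.09 = 0.193
- Slope: 0.128 SD towards benefit, matching the simulated 0.128

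The slope is per unit of adherence. The like-for-like planned effect is 0.25 / 0.77 = 0.325, so the spurious slope is 0.128 / 0.325 = 39% of it.

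**4. Null simulations, 100 per arm, correlation 0.2 to 0.3.**

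| Mean (SD) of adherence | Spurious slope, SD units | Share of planned effect at full adherence | Two-sided error |
|---|---|---|---|
| 0.90 (0.1) | 0.028 to 0.042 | 10–15% of 0.278 | about 5–7% |
| 0.80 (0.2) | 0.064 to 0.096 | 20–31% of 0.3125 | about 9–13% |
| 0.77 (0.3) | 0.085 to 0.128 | 26–39% of 0.325 | about 12–22% |

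The middle row is 0.12 to 0.18 on the square-root scale, divided by 1.87.

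A normal approximation gives similar upper ends. The standard error is 0.632 / √(200 × Var(A)).

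- 0.90 (0.1): 0.632 / √(200 × 0.2075) = 0.098; shift 0.042 / 0.098 = 0.43; error about 7%
- 0.80 (0.2): 0.632 / √(200 × 0.18) = 0.105; shift 0.096 / 0.105 = 0.91; error about 15%
- 0.77 (0.3): 0.632 / √(200 × 0.193) = 0.102; shift 0.128 / 0.102 = 1.26; error about 24%

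The upper ends are therefore good to about two percentage points and depend on the shape assumed for adherence.

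**5. Direction.** When the correlation favours the drug, nearly all the excess is false benefit: 4.8% and 6.4% in the first setting, against a nominal 2.5%. When its sign reverses, the bias is equal and opposite. At −0.3, false benefit falls below 1% and most rejections are false harm.

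**6. The alternative on the same data.** With placebo exposure at 0, using arm as the instrument amounts to dividing the between-arm difference in change by mean tamoxifen adherence. Its mean stayed within 0.003 SD of zero in every scenario. Its spread was about 1–12% wider in simulation. The large-sample ratio √(1 + 2(s/m)²) gives 1%, 6% and 14% for the three settings.

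**The case against.** The strongest reply is that nothing decisive rests on this model. It is an addition to the intention-to-treat analysis and has no significance rule of its own. Its interpretive sentence is conditional: it says what an effective drug might produce, not that a decrease proves efficacy. All of that stands. A reader might infer that the plan offers the as-treated result as proof of efficacy, or that a misleading result could make the trial positive. The text supports neither.

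A reader might also take the zero for placebo as the error. It is not: zero is the true tamoxifen exposure of a woman on placebo, and placebo pill counts are analysed elsewhere. The fault is removing the arm and then reading observed adherence as though it had been assigned.

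The size is also open to challenge. With adherence near 90% and little spread, about 98% of the variance of the regressor comes from the randomised contrast (0.2025 / 0.2075), so inflation is small. The 77% in Section 12.5 is a detectable alternative, not an expectation.

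Finally, the instrumental estimate adds almost nothing to the intention-to-treat test, does not explore how response varies with adherence, and needs assumptions of its own. That argues for keeping the as-treated model as description, not for letting it carry the inference.

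**Conclusion.** The point holds as a limitation of a supplementary analysis. The as-treated coefficient is biased whenever adherence is associated with density change for reasons other than the drug, and the direction cannot be known beforehand. The error rates range from barely above nominal (about 5–7% at 0.90, SD 0.1) to serious (about 12–22% at 0.77, SD 0.3).

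These figures rest on assumed SDs and correlations, overall rather than time-specific adherence, and complete data. Sections 6.3 and 14.3 end participation after more than 90 consecutive days off drug. That narrows the range of adherence and adds selection, neither of which was modelled.

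The primary analysis, the effectiveness criteria and the sample size are unaffected. To read this as a threat to the trial's main conclusion, or as a bias only towards benefit, goes beyond what the documents support.

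**What to change.** In Section 12.4, base the noncompliance inference on an estimate that uses randomised arm as the instrument for pill-count adherence, with a bootstrap interval. State its assumptions: assignment acts only through drug taken, response is linear in adherence, and pill counts are accurate. Say how women without year-2 mammograms are handled, since a simple change-score version would lose women whom the planned mixed model keeps.

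Fit the same adherence regression within the placebo arm as a negative control, using pill counts already collected. An association there would show that adherence tracks density without the drug.

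If the as-treated model is kept, label it descriptive and not evidence of efficacy.

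The cost is a change to the analysis text, one or two extra models and a slightly wider interval (about 1–12% in simulation). No new data, visits or participants are needed.

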The estimates from linear mixed effects model are valid in the presence of incomplete response data if missing data occurs at random. However, non-participation and dropouts may occur differentially between treatment groups for various reasons, possibly resulting in non-ignorable missing data. In addition to collecting information on reasons for nonparticipation, we will apply two analytic approaches to examine the effects of missing data on study results [104]: 1) pattern mixture models and 2) selection models. In pattern mixture models, the four possible missing data patterns (arising from 3 time points with no missing data at t0 and considering a response as missing if data from both breasts are missing) will be used as covariates in the above-described bivariate linear mixed effects model. The effects of missing data on the estimate of treatment effect can be assessed. An overall estimate of the treatment effect may be obtained by averaging the estimates over the missing pattern groups. In selection model, we will model the probability of dropout using baseline covariates to estimate the propensity for dropout. The propensity scores will be used as a covariate in the bivariate linear mixed effects model to adjust for the effects of dropout on treatment effects.

Secondary efficacy objectives will be evaluated by applying the methods for longitudinal analysis as described below. Significance of the low dose tamoxifen effects is evaluated in the manner described above based on testing the significance of the interaction of time by group indicator variables. The distribution of continuous variables will be

examined graphically and appropriate transformations made before applying analytical methods based on normal assumption.

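### Neither analysis planned to examine non-ignorable dropout does so adequately: the selection model is a missing-at-random adjustment, and the pattern-mixture model is under-specified at t2

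*Combined protocol and SAP*

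**What the plan says.** Section 12.4 of the combined protocol and SAP (Aim 1, mammographic breast density) states the assumption behind the primary model: "The estimates from linear mixed effects model are valid in the presence of incomplete response data if missing data occurs at random". It then gives the worry: "non-participation and dropouts may occur differentially between treatment groups for various reasons, possibly resulting in non-ignorable missing data". Two approaches follow.

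- **Pattern mixture.** The plan counts "the four possible missing data patterns (arising from 3 time points with no missing data at t0", treating a visit as missing only if both breasts are missing. These patterns "will be used as covariates in the above-described bivariate linear mixed effects model". It adds: "An overall estimate of the treatment effect may be obtained by averaging the estimates over the missing pattern groups".
- **Selection model.** Here, "we will model the probability of dropout using baseline covariates to estimate the propensity for dropout". Then: "The propensity scores will be used as a covariate in the bivariate linear mixed effects model to adjust for the effects of dropout".

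The section gives no interaction of pattern with time or treatment, no averaging weights, no identifying restriction and no delta or tipping-point analysis. Reasons for non-participation will be collected, but no use of them in a model is described.

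**The concern.** A check on non-ignorable dropout must let the unseen densities differ from what the observed data predict. It must also say by how much, or under what restriction. As written, one of the two analyses does not allow this. The other either allows it only trivially or leaves the key assumption to the analyst.

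The effect at t2 is what matters, because Section 12.4 defines success through the time-by-treatment terms. Section 12.5 expects 10% attrition at each annual visit, so 1 - 0.9 x 0.9 = 19% of women would lack t2 data. Treatment-related loss is plausible: Section 6.3 takes women off therapy for specified toxicities, and Section 14.3 withdraws women who are off medication for more than 90 consecutive days. If such losses are related to density, the planned checks could sit close to the primary estimate and say little about its bias.

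**Working it through.** **Inputs from Section 12.5.** Two-sided alpha 0.05; power 0.80; compound symmetry with correlation 0.8; effect size 0.25 SD at t2; 10% attrition per visit; 115 women per arm. The treatment-by-time coefficient of 0.2338 per year gives 0.2338 x 2 = 0.468 at t2 on the square-root scale (RTMBD), so one SD is 0.468 / 0.25 = 1.87.

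**Reproducing the plan's figure.** For the linear contrast without attrition, n = 2(1.960 + 0.842)^2 x 2(1 - 0.8) / 0.25^2 = 100.5 per arm, against 100 stated. With retention 1, 0.9 and 0.81, the factor 2(1 - 0.8) = 0.4 becomes 1 + 1/0.81 - 2(0.8)/sqrt(0.81) = 0.457. This gives n = 114.7, against 115 stated. The planning inputs are therefore read correctly.

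**Selection model.** A selection model for non-ignorable dropout lets the probability of dropping out depend on the unseen outcome. Here it depends on baseline covariates only, and the score enters a likelihood-based model that already assumes missing at random. The assumption is unchanged.

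**Pattern mixture, literal reading.** A pattern main effect shifts a woman's level, which her random effects largely absorb already. The time-by-treatment terms come mostly from within-woman change, so they barely move.

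This was simulated with 115 women per arm, a woman-level outcome in SD units, a true t2 effect of -0.25, monotone dropout and 200 runs per scenario. Placebo dropout was 10% per visit. In the two outcome-dependent scenarios, the tamoxifen dropout logit was logit(0.1) + 2 x (standardised unseen change) - 0.9, so women whose density fell less were likelier to leave. The change was either the whole two-year change or the change since the previous visit. These mechanisms are assumptions; the documents give only the attrition rate.

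| t2 effect (SD units) | Random dropout | Two-year change | Change since last visit |
|---|---|---|---|
| Full data | -0.258 | -0.245 | -0.250 |
| Mixed model | -0.256 | -0.385 | -0.372 |
| + pattern main effects | -0.256 | -0.386 | -0.373 |
| + pattern-by-time terms | -0.256 | -0.385 | -0.369 |
| + propensity covariate | -0.256 | -0.393 | -0.378 |
| Pattern-by-arm slopes, averaged | -0.254 | -0.271 | -0.536 |

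Monte Carlo error is about 0.006 (0.009 in the last row). A separate simulation of outcome-dependent tamoxifen dropout on the RTMBD scale gave -0.470 with full data, -0.674 from the mixed model and -0.676 with pattern covariates. The bias there is 0.204; adding the patterns moved the estimate by 0.002.

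**Pattern mixture, averaging reading.** The observed visits per arm are 3 (complete), 2 (t2 missing), 2 (t1 missing) and 1 (both missing), so 8 of 12 pattern-by-visit cells. Under the unstructured mean, the t2 treatment effect can be estimated only in the two patterns with a t2 mammogram. Under the linear model it needs two visits, so it can be estimated in three of four. The last row of the table uses the linear model and lets women with both visits missing borrow the slope of those missing only t2. That choice nearly removed the bias in one scenario and worsened it in the other.

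**How much departure would matter.** The planned standard error is 0.25 / 2.802 = 0.089 SD. Suppose unseen t2 values of tamoxifen dropouts are worse than predicted by delta SD. The effect becomes 0.25 - 0.19 x delta. An observed 0.25 SD effect loses significance at delta = (0.25 - 1.960 x 0.0892) / 0.19 = 0.40 SD (0.395 x 1.87 = 0.74 RTMBD units) and reaches zero at 0.25 / 0.19 = 1.3 SD. Power is 74%, 62%, 41% and 10% at delta of 0.1, 0.25, 0.5 and 1.0. The documents give no value for delta.

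**The case against.** The strongest reply is that pattern-mixture models are a recognised non-ignorable family. This stands. A reader might infer that both planned analyses stay within missing at random, and the text does not support that. Even a pattern main effect changes the t2 prediction for given t0 and t1 values, by 1 - 2(0.8)/(1 + 0.8) = 0.11 SD per 1 SD of pattern shift. The averaging sentence also makes sense only if effects differ by pattern, and under that reading the estimate can move well away from the mixed model. It does not follow that the check works, since the direction of the move rests on a restriction the plan does not state.

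It can also be said that the linear model rescues averaging. It does so in part: one pattern remains unidentified instead of two.

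A reader might try to prove the point by supposing that tamoxifen dropouts return to placebo-like density after leaving. If dropout is unrelated to outcome and the return occurs only in unseen values, the observed data are the same with or without it. No model of those data could reveal it, so the example is not evidence against these two analyses.

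Nor do the documents say that agreement between the analyses will be reported as proof of robustness. They say only that the effect of missing data can be assessed. Further detail may lie in the cited methods reference, which was not available.

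**Conclusion.** The concern holds in two parts. First, the propensity analysis carries a selection-model label but is a missing-at-random adjustment. Following the plan exactly would not probe "possibly resulting in non-ignorable missing data", so this is a wrong method for the stated purpose, not just missing detail. Second, the pattern-mixture analysis is nearly blind when read literally and not fully identified at t2 when read generously.

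The first part rests on the plan's wording alone. The near-blindness rests on simulations with assumed mechanisms: the size of bias in them is illustrative, while the near-equality of the mixed-model and pattern-covariate estimates is the finding. The identification result is a count of observed cells and needs no such assumption.

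A reader might infer that the primary analysis is invalid or that its effect will be overstated. The documents do not show that dropout will depend on unseen density; they only raise the possibility. The primary model can stand, but its stated safeguard should be repaired.

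**What to change.** 1. Describe the propensity analysis as a covariate adjustment under missing at random.
2. If the pattern-mixture model is kept, write out the pattern-by-time-by-treatment terms, the identifying restriction for each pattern without t2 data under both mean structures, and the averaging weights.
3. Add a delta-adjusted tipping-point analysis of missing t1 and t2 RTMBD, with delta varied by arm. Report where each of the plan's two routes to success (the 2-df test and the t2 interaction) ceases to be significant. On the planning figures, a tamoxifen-arm range from 0 to about 1.3 SD would cover both loss of significance and a null effect. The collected reasons for dropout can help judge which values are plausible. Placebo-reference imputation is one optional scenario.

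Both existing models may stay once relabelled and specified; replacing them is not required. The cost is SAP text and some programming, with no new data. The text should be settled before unblinding.
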